5.2 Clinical Laboratory Evaluations

A total of 16 mL blood will be collected for screening clinical labs for the evaluation of eligibility. If screening laboratory results are out of range value, they may be repeated once provided there is an alternative explanation for the out of range value. Participants must have acceptable screening laboratory findings prior to enrollment. The acceptable ranges for study eligibility are listed in Appendix B.

For the assessment of safety, a total of 12.5 mL of blood will be collected for clinical safety labs on Day 1 (pre-vaccination) and the Day 8 (7-days post dose #1) visit. This evaluation is to include a CBC with differential for total white blood cells (WBC) count, hemoglobin (Hg), absolute neutrophil count (ANC), platelet count, creatinine, aspartate aminotransferase (AST),

alanine aminotransferase (ALT), total bilirubin (TBIL), and C-reactive protein (CRP). On Day 2 (one day after receipt of the first dose of vaccine), a 3.5 mL volume of blood will be collected for the assessment of C-reactive protein only. The grading of toxicity for the clinical safety lab values that are not in the normal range is provided in Appendix C.

Due to the U.S. Public Health Emergency with COVID-19, SARS-CoV-2 testing will be performed on the days of scheduled vaccination. These test results are not intended to inform the eligibility of participants for vaccination, as the results are likely to be available after 2-3 days. However, for possible pre-symptomatic participants (i.e., eligible due to the absence of symptoms at the time of vaccination) the positive test result could be used to provide an alternate etiology for the development of symptoms due to COVID-19 rather than due to the study product. The test results of acute infection (positive PCR) or prior infection (positive antibody) will also be used in planned stratified analysis of the immunology outcomes, as COVID-19 infection may alter the immune response to vaccination. The results of SARS-CoV-2 testing will be provided to participants at their Day 7 and Day 36 visits. If SARS-CoV-2 testing results are received prior to these visits, the research team may call participants to report these results.

All women of child-bearing potential will have a serum pregnancy test performed during screening and a urine pregnancy test on the vaccination days. The results of the urine pregnancy test must be negative prior to enrollment in the study, and prior to each vaccination.

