7.2 Methods and Timing for Assessing, Recording, and Analyzing Safety Parameters

Adverse Event (AE): ICH E6 defines an AE as any untoward medical occurrence in a patient or clinical investigation subject administered a pharmaceutical product regardless of its causal relationship to the study treatment. An AE can therefore be any unfavorable and unintended sign (including an abnormal laboratory finding), symptom, or disease temporally associated with the use of medicinal (investigational) product. The occurrence of an AE may come to the attention of study personnel during study visits and interviews of a study recipient presenting for medical care, or upon review by a study monitor.

All AEs including local and systemic reactions not meeting the criteria for "serious adverse events" should be captured on the appropriate CRF. Information to be collected includes event description, time of onset, clinician's assessment of severity, relationship to study product (assessed only by those with the training and authority to make a diagnosis, which would include MD, PA, and Nurse Practitioner, listed on the FDA Form 1572), and time of resolution/stabilization of the event. All AEs occurring while on study must be documented appropriately regardless of relationship. All AEs will be followed to adequate resolution.

Any medical condition that is present at the time that the patient is screened should be considered as baseline and not reported as an AE. However, if it deteriorates at any time during the study, it should be recorded as an AE.

Special Circumstance of COVID-19 Pandemic. While there is a U.S. Public Health Emergency for COVID-19, there is the risk of community transmission of infections. The testing of both anti-SARS-CoV-2 antibody and presence of virus by PCR on the days of vaccination (both dose #1 and #2) are intended to provide the investigators with information on potential asymptomatic or presymptomatic infections at vaccination, but the results will not be available in time prior to vaccination. Therefore, the results are intended to potentially provide alternate etiology for reactogenicity that might be observed post-vaccination which could be due to a COVID-19 infection rather than to the study product. The results of SARS-CoV-2 testing will be provided to participants at their Day 7 and Day 36 visits. If SARS-CoV-2 testing results are received prior to these visits, the research team may call participants to report these results.

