Severity of Event: All AEs will be assessed by the clinician using a protocol defined grading system. For events not included in the protocol defined grading system, than the following guidelines will be used to quantify intensity.

- Mild – Grade 1: events require minimal or no treatment and do not interfere with the patient's daily activities.
- Moderate – Grade 2: events result in a low level of inconvenience or concern with the therapeutic measures. Moderate events may cause some interference with functioning.
- Severe – Grade 3: events interrupt a patient's usual daily activity and may require systemic drug therapy or other treatment. Severe events are usually incapacitating.

Changes in the severity of an AE should be documented to allow an assessment of the duration of the event at each level of intensity to be performed. Adverse events characterized as intermittent require documentation of onset and duration of each episode.

Relationship to Study Product: The clinician's assessment of an AE's relationship to Vaccine is part of the documentation process, but it is not a factor in determining what is or is not reported in the study. If there is any doubt as to whether a clinical observation is an AE, the event should be reported. All AEs must have their relationship to study product assessed using the terms: related or not related. In a clinical trial, the study product must always be suspect. To help assess, the following guidelines are used.

- Related – The event is temporally related to the administration of the study product and no other etiology explains the event.
- Not Related – The event is temporally independent of study product and/or the event appears to be explained by another etiology.

Serious Adverse Event (SAE): An adverse event or suspected adverse reaction is considered "serious" if, in the view of either the investigator or sponsor, it results in any of the following outcomes:

- Death,
- a life-threatening adverse event*,
- inpatient hospitalization or prolongation of existing hospitalization,
- a persistent or significant incapacity or substantial disruption of the ability to conduct normal life functions, or

- a congenital anomaly/birth defect.

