7.3 Halting Rules

If any of the following halting rules are met, the study will not proceed with the remaining enrollment or dose escalation without a review by and recommendation from an Independent Safety Monitoring Committee:

- Two or more subjects in a dosage cohort experiences the same systemic toxicity, except for fever, of grade 3 or above and judged to be associated with vaccine.
- Two or more subjects in a dosage cohort experiences a fever at or greater than grade 3 within 7 days of vaccination.
- Two or more subjects in a dosage cohort experiences the same grade 2 or greater abnormal laboratory value and judged to be associated with vaccine.
- Three or more subjects in a dosage cohort experience the same localized toxicity (local pain or induration) at grade 3 or above judged to be associated with vaccine.
- Any death occurring within 7 days following administration of vaccine that was not the result of trauma or accident.
- Any subject experiences an SAE determined to be related to vaccine.

The study may also be halted due to PI or Sponsor discretion.

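### The 7.2 relatedness scale could let a SARS-CoV-2 result take a vaccine-caused event out of the attribution-based halting counts; the effect is small, and separately the scheduled SMC review stops 7 days after dose 1

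*Combined protocol and SAP*

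**What the plan says.** Section 7.2 (Relationship to Study Product) has two terms. Related means "The event is temporally related to the administration of the study product and no other etiology explains the event". Not Related applies when the event is temporally independent of the product, or when "the event appears to be explained by another etiology"; either condition is enough. The same paragraph calls these guidelines and says the product should always be under suspicion.

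Section 7.2 (COVID-19 circumstance) describes "The testing of both anti-SARS-CoV-2 antibody and presence of virus by PCR on the days of vaccination" and says "the results are intended to potentially provide alternate etiology for reactogenicity that might be observed post-vaccination". Section 5.2 says that for possibly pre-symptomatic participants "the positive test result could be used to provide an alternate etiology for the development of symptoms due to COVID-19". Section 10.2 places the testing in Cohort C, and the Appendix A schedule covers Cohorts C and D.

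In Section 7.3, the non-fever systemic rule needs two or more participants in a dosage cohort with "the same systemic toxicity, except for fever, of grade 3 or above and judged to be associated with vaccine". The SAE rule needs one SAE determined to be related. The grade 3 fever rule and the death rule carry no attribution condition. A met rule stops remaining enrollment or dose escalation until the SMC has reviewed.

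Section 7.4 schedules SMC review of data up to 7 days after the first dose in each cohort. Section 2.1 gives the main purpose of two doses as finding out whether the second dose raises the risk of reactogenicity.

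**The concern.** An event with two plausible causes leans toward Not Related, because an apparent alternative is enough. The COVID-19 symptoms listed under exclusion criterion 5 (Section 3.2) include fever, chills, fatigue, muscle or body aches, headache and nausea. All six are also solicited systemic reactions in Section 7.1, and five of them are not fever, so they fall under the attribution-dependent rule. Section 5.2 expects results after 2 to 3 days, so they can be in hand when causality is judged at Day 8 or Day 36.

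With a threshold of two participants, setting aside one vaccine-caused event can prevent a pause. Under Section 2.2 the scheduled SMC review comes after a cohort has finished enrolling, so it cannot stand in for a pause during enrollment. After dose 2, non-serious non-fever events have no scheduled SMC review under 7.4.

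**Working it through.** **No plan figure to reproduce.** Section 10.1 says the sample size was not derived for a stated power, and the documents give no halting probabilities, test-positivity rates or rates for this vaccine.

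**Inputs from the documents**
- Cohort C (Section 2): 6 + 4 + 6 + 4 + 2 = 22, of whom 20 receive vaccine. At 25 µg there are 6 + 6 = 12. Two vaccine doses go to 6 + 4 = 10, of whom 6 are at 25 µg.
- Trigger (Section 7.3): 2 participants for the non-fever systemic rule, 1 for a related SAE. Dosage cohort can mean the dose level or the whole cohort, so both sizes are shown.

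**Assumptions**
- p is the true per-participant rate of the same vaccine-caused grade 3 non-fever systemic event: 1%, 5% or 20%. The nearest anchor is Section 1.4, which lists myalgia and arthralgia at 0.1% to under 1% for the licensed Vi component alone. The trivalent product could be higher.
- q is the share of those vaccine-caused events judged Not Related because of a positive test: 0%, 2% or 5%.

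**Formula.** P(trigger) = P(X ≥ 2), X ~ Binomial(n, p(1 − q)).

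Example, n = 10, p = 20%:
- q = 0: 1 − 0.80^10 − 10(0.20)(0.80^9) = 1 − 0.1074 − 0.2684 = 0.624.
- q = 5%, so p(1 − q) = 0.19: 1 − 0.81^10 − 10(0.19)(0.81^9) = 1 − 0.1216 − 0.2852 = 0.593.

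| Group | p | q = 0 | q = 2% | q = 5% | Loss at q = 5% (points) |
|---|---|---|---|---|---|
| Dose 2, 25 µg, n = 6 | 1% | 0.15% | 0.14% | 0.13% | 0.01 |
| | 5% | 3.3% | 3.2% | 3.0% | 0.3 |
| | 20% | 34.5% | 33.5% | 32.0% | 2.5 |
| Dose 2, all two-dose, n = 10 | 1% | 0.43% | 0.41% | 0.39% | 0.04 |
| | 5% | 8.6% | 8.3% | 7.9% | 0.7 |
| | 20% | 62.4% | 61.2% | 59.3% | 3.1 |
| Dose 1, 25 µg, n = 12 | 1% | 0.62% | 0.59% | 0.56% | 0.06 |
| | 5% | 11.8% | 11.4% | 10.9% | 1.0 |
| | 20% | 72.5% | 71.4% | 69.6% | 2.9 |
| Dose 1, all vaccinees, n = 20 | 1% | 1.7% | 1.6% | 1.5% | 0.16 |
| | 5% | 26.4% | 25.7% | 24.5% | 1.9 |
| | 20% | 93.1% | 92.5% | 91.6% | 1.5 |

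Searching over all p at q = 5%, the largest loss is 3.4 points for n = 6 and 2.9 to 3.1 points for the other sizes.

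**Given exactly two qualifying events**, the trigger is missed with probability 1 − (1 − q)²: 1 − 0.98² = 4.0% at q = 2%, and 1 − 0.95² = 9.8% at q = 5%.

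**Related-SAE rule** (trigger of 1), n = 20, p = 5%, q = 5%: 1 − 0.95^20 = 64.2% falls to 1 − 0.9525^20 = 62.2%.

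**The case against.** The strongest reply is that clinicians are told to keep the product under suspicion and that nothing makes a positive test decisive. That stands. A reader might infer that a positive test automatically removes an event; the text says only that it could or might potentially supply a cause.

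Second, most of 7.3 speaks of association with vaccine, and only the SAE rule says related. The link to 7.2 is therefore an inference. It is a reasonable one, because 7.2 holds the only relatedness scale in the protocol.

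Third, a reader might extend the point to the laboratory rule, "the same grade 2 or greater abnormal laboratory value and judged to be associated with vaccine". The documents do not clearly support that: 5.2 offers the test for symptoms and 7.2 for reactogenicity, which 7.1 lists apart from laboratory values. Nor do they clearly support treating a past-infection antibody as a cause. Section 7.2 mentions both tests, but ties them to possible asymptomatic or pre-symptomatic infection at vaccination. Section 5.2 labels a positive antibody as prior infection and uses it for the stratified immunology analysis.

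Fourth, several safeguards need no attribution: the fever and death rules, the grade 2 or higher solicited-event criterion in 10.3, SMC review of dose-1 data, and safety monitor and SMC review of all SAEs. The investigator or sponsor may also halt at discretion. Any two grade 3 events in the same solicited category already meet 10.3, which is not limited to dose 1.

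On dose 2, the objection is that this issue is separate from the definition, and that is correct. A trigger after dose 2 may have little enrollment left to stop in Cohort C, and Cohort D may not run. Section 2 also plans an interim safety analysis of 28-day data before Part 2, though it does not say which dose that follows or that the SMC receives it. Section 2.2 says only post-vaccination where 7.4 says post-first dose, and the meeting schematic is not shown in the text available. These points reduce the gap but do not close it.

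**Conclusion.** Minor, and worth correcting because it is cheap. The scale in 7.2 yields to any apparent alternative, and the protocol names one that overlaps the solicited symptoms. Applied through 7.3, this could remove a vaccine-caused event from the non-fever systemic count or the related-SAE rule in Cohort C, or in D if it opens. For the two-participant trigger in Cohort C, the loss is under 0.2 points at a 1% event rate and about 3 points at most at 20%, with 2% to 5% set aside. All these rates are assumed. Setting aside an event truly caused by COVID-19 is correct and is not counted as a loss.

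A reader might infer that the halting rules are seriously weakened. That would need a much larger share set aside. At 20%, for instance, the n = 10, p = 20% case falls from 62.4% to 49.2%. A share of that size might follow if past-infection antibody were accepted as a cause, which the text does not clearly do. A reader might also infer that second-dose safety goes unmonitored. It does not: events are collected and tabulated, the fever rule applies within 7 days of vaccination, and all SAEs are reviewed. What is missing is a scheduled SMC look at second-dose reactogenicity.

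**What to change.** 1. In 7.2, define Related as a reasonable possibility that the product caused the event. Add that a positive SARS-CoV-2 result alone does not make a temporally associated event Not Related.
2. Give the SMC each 7.3 count with and without attribution.
3. In 7.4, include Cohort C data through 7 days after dose 2 in the SMC review before Part 2, so that the post-dose-2 table has a meeting to receive it.

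Thresholds stay unchanged. The cost is two sentences in 7.2, one in 7.4, one extra column and one extra table. Some background illness may count as related and prompt an additional SMC review. The review before Part 2 would wait for the last Cohort C participant's Day 36 visit rather than Day 8, which is 36 − 8 = 28 days later. Part of that wait may already be absorbed by the planned interim analysis of 28-day data.

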7.3 Halting Rules

If any of the following halting rules are met, the study will not proceed with the remaining enrollment or dose escalation without a review by and recommendation from an Independent Safety Monitoring Committee:

- Two or more subjects in a dosage cohort experiences the same systemic toxicity, except for fever, of grade 3 or above and judged to be associated with vaccine.
- Two or more subjects in a dosage cohort experiences a fever at or greater than grade 3 within 7 days of vaccination.
- Two or more subjects in a dosage cohort experiences the same grade 2 or greater abnormal laboratory value and judged to be associated with vaccine.
- Three or more subjects in a dosage cohort experience the same localized toxicity (local pain or induration) at grade 3 or above judged to be associated with vaccine.
- Any death occurring within 7 days following administration of vaccine that was not the result of trauma or accident.
- Any subject experiences an SAE determined to be related to vaccine.

The study may also be halted due to PI or Sponsor discretion.

7.4 Safety Oversight

Safety oversight will be under the direction an Independent Safety Monitoring Committee (SMC). There will be an Independent Safety Monitor (ISM) who will be independent of the study team, local to the study site and will be provided access to study records, if required. The SMC will be comprised of the ISM plus at least two independent members with expertise in infectious

diseases and/or clinical trials who will advise the Sponsor and the PI. SMC quorum is defined as a simple majority. The SMC will be responsible for three scheduled meetings to review the available data up to 7-days post-first dose of vaccination for each Cohort; for Cohorts A-C, the SMC will determine whether the trial may proceed to the next dosage cohort. The ISM will review all SAEs in real time and provide a written ISM assessment regarding the event. The SMC may receive a final study report, but a recommendation will not be necessary.

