2 STUDY DESIGN

Part 1. The first part of the study will be conducted as a traditional first-in-human, double-blinded, randomized, placebo-controlled, dose-escalation study. This part of the study is designed to assess the safety, reactogenicity, and preliminary immunogenicity of a single parenteral (i.e., intramuscular) dose of a trivalent (S. Enteritidis/S. Typhimurium/S. Typhi) conjugate vaccine in comparison to a placebo control consisting of buffer plus preservative (2-phenoxyethanol).

In total, approximately 44 healthy eligible participants will be sequentially enrolled into Part 1 of the study in three steps based on dose.

In **Step 1** (Cohort A), 10 participants will be randomly allocated to one of two treatment groups to receive:

- trivalent vaccine, 6.25 mcg of each COPS and Vi, in 0.125 ml volume (N=8) mixed with 0.375 ml of placebo (phosphate buffered saline + 2-phenoxyethanol + Tween 80 stabilizer) to reach a volume of 0.5 ml;
- or placebo, 0.5 ml volume (N=2).

In **Step 2** (Cohort B), 12 participants will be randomly allocated to one of two treatment groups to receive:

- trivalent vaccine, 12.5 mcg of each COPS and Vi, in 0.25 ml volume (N=10) mixed with 0.25 ml of placebo to reach a volume of 0.5 ml;
- or placebo, 0.5 ml volume (N=2).

In **Step 3** (Cohort C), 22 participants will be randomly allocated to one of five treatment groups to receive:

- one dose of trivalent vaccine, 25 mcg of each COPS and Vi, in 0.5 ml volume (N=6);
- one dose of trivalent vaccine, 12.5 mcg of each COPS and Vi, in 0.5 ml volume (N=4);
- two doses of trivalent vaccine, 25 mcg of each COPS and Vi, in 0.5 ml volume (N=6);
- two doses of trivalent vaccine, 12.5 mcg of each COPS and Vi, in 0.5 ml volume (N=4);
- or placebo, 0.5 ml volume (N=2).

Each of the escalated dosage cohorts is designed to be slightly larger in size in order to have a higher probability to detect potential reactogenicity with the increasing quantities of flagellin, which is a component (the protein carrier of the NTS conjugates), while increasing the number of subjects exposed in a step-wise fashion.

Following collection of the 28 day post-vaccination clinical data and rapid measurement of serum IgG ELISA antibody levels, there will be an interim analysis of the safety and immunogenicity in preparation for advancement to Part 2 of the study.

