Serological data demonstrate that a single dose of monovalent Typbar-TCV conjugate administered to Indian children 6-23 months of age is highly immunogenic in stimulating Vi antibodies and the titers remain elevated for up to 5 years post primary-immunization. There are no published or public human data to dictate the serum antibody response to a conjugate vaccine consisting of COPS conjugated to a carrier protein. Moreover, adult humans immunized with a glycoconjugate vaccine of any sort typically mount a maximal antibody response after the first dose that is not boosted following administration of a second dose of glycoconjugate. Therefore, the main purpose of administering two-sequential doses of trivalent conjugate separated by 4 weeks is to evaluate whether a two-dose regimen presents an increased risk for reactogenicity when the second dose is administered. A second dose is not expected to increase anti-COPS titers in U.S. adults but it may perhaps increase antibody avidity.

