2.2 Work flow of the Phase 1 study in U.S. adults

Eligible subjects will be screened, enrolled, and vaccinated at the CVD Outpatient Vaccine Clinic (located on the 4th floor of HSF1) or Pharmaron (located in the UMB BioPark 1 building). After the documentation of informed consent, subjects will be screened for eligibility; eligible subjects will subsequently be enrolled and randomized to a treatment group. On Day 1 (and Day 29, for participants in Cohorts C and D), study product will be administered, in double-blinded fashion, as an intramuscular injection into the deltoid muscle. Following vaccination, there will be a 20-minute post-vaccination observation period. Following each dose of study product, safety and reactogenicity will be measured by a daily oral temperature and solicited AE reporting over the subsequent 7 days (via a 7-day memory aid); unsolicited AE reporting will occur through 28 days following the last dose of vaccine. The occurrence of any SAEs will be recorded through 6 months after the last dose of vaccine (Day 180 or 210, for participants in Cohort C and D).

Subjects in Steps 1-2 (Cohorts A-B) will complete four additional outpatient visits on Days 8, 29, 57, and 180 (final visit). Subjects in Cohorts C and D will complete five additional outpatient visits on Days 8, 29 (second dose of masked study product), 36, 57, and 210 (final visit). The recording of AEs and concomitant medication change information, the performance of a physical exam (if indicated), and the collection of study-specific samples will be performed during these outpatient visits. Clinical safety laboratory tests will be evaluated on Day 8. The final study visit will be for the collection of SAE information (Day 180 or 210).

After the completion of enrollment of each cohort, the safety data through 7-days post-vaccination are to be reviewed by an independent Safety Monitoring Committee (SMC). The SMC must provide approval prior to the enrollment of the subsequent dose-escalating cohort. Immunology data may not be available at the times of these scheduled SMC reviews.

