In addition to the evaluation of safety, immunogenicity assessments are planned to evaluate the immune responses induced by the three different vaccine formulations. The study, however, is not statistically powered to determine significance of any pre-specified difference. Therefore, there was no formal sample size calculation, based on immunogenicity, as the basis for the designed study. Nonetheless, the sample size was chosen based on the number of subjects appropriate for a phase 1 study in which these vaccines have never been evaluated in humans.

[figure not shown]
Schematic of Study Cohorts

Cohort	Vaccine	Dose of each COPS and of Vi (µg)	No. Subjects	Dose #1	Dose #2	Vaccination Days
A (Step 1)	Trivalent Placebo	6.25 0	8 2	Vaccine Placebo	- -	1
SMC review of available safety data through 7-days post-vaccination before proceeding to the next dosage cohort						
B (Step 2)	Trivalent Placebo	12.5 0	10 2	Vaccine Placebo	- -	1
SMC review of available safety data through 7-days post-vaccination before proceeding to the next dosage cohort						
C (Step 3)	Trivalent	25	6	Vaccine	Vaccine	1& 29*
	Trivalent	25	6	Vaccine	Placebo	1 & (29)*
	Trivalent	12.5	4	Vaccine	Vaccine	1& 29*
	Trivalent	12.5	4	Vaccine	Placebo	1 & (29)*
	Placebo	0	2	Placebo	Placebo	1 & (29)*
SMC review of available safety data through 7-days post-vaccination before proceeding to Part 2 of the study						
D (Expanded, confirmatory cohort)	Trivalent	(highest, well-tolerated dose among cohorts A-C)	25	Vaccine	Vaccine	1 & 29*
	Trivalent		25	Vaccine	Placebo	1 & (29)*
	Placebo		10	Placebo	Placebo	1 & (29)*
Total			N = 104			

* In cohorts C and D, the trivalent vaccine will be administered as a single dose (day 1) or as a two-dose (days 1 and 29) regimen. In order to maintain the masking of study products, on day 29 a placebo will be administered when indicated by the parentheses.

SMC, Safety Monitoring Committee

Schematic of the Flow of the Cohort enrollments and timing of SMC meetings:

Cohort D

Trivalent on day 1, (placebo on day 29);
Trivalent on day 1 and day 29;
Or Placebo on day 1 and day 29

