10.1.1 Sample size in Part 2 of the study

The adaptive design for the Part 2 portion of this study will involve the evaluation of single dose vs. two-dose regimens of the trivalent vaccine, in comparison to placebo. There is a theoretical possibility of immunological “interference” with the addition of antigens in multivalent glycoconjugate vaccines.⁵¹ Under such circumstances, the responses to some antigens may be reduced. There is no expectation for there to be differences in the seroconversion rates between single dose and two-dose regimens of glycoconjugate vaccines in healthy U.S. adults.⁵² On the other hand, the design of Part 2 of the study will substantiate moving forward with two-dose regimens in sub-Saharan Africa where we do expect that more than a single dose will be required in the target pediatric population^{53,54}—so the purpose is the demonstration of safety with two sequential doses and not for showing differences in immune responses.

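### No scheduled SMC review of Cohort C second-dose reactogenicity is required before Part 2 opens, and a met halting rule does not expressly stop second doses already due

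*Combined protocol and SAP*

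**What the plan says.** **Purpose of the second dose.** Section 2.1 states that "the main purpose of administering two-sequential doses of trivalent conjugate separated by 4 weeks is to evaluate whether a two-dose regimen presents an increased risk" of reactogenicity at the second dose. Section 10.1.1 says of Part 2 that "the purpose is the demonstration of safety with two sequential doses and not for showing differences in immune responses".

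**Scheduled SMC review.** Section 7.4 gives the SMC three scheduled meetings to "review the available data up to 7-days post-first dose of vaccination for each Cohort", and has it decide on progression after Cohorts A to C. The only later item for the committee there is this: "The SMC may receive a final study report, but a recommendation will not be necessary". The cohort schematic in Section 2.2 places an "SMC review of available safety data through 7-days post-vaccination before proceeding to Part 2 of the study". Neither the schematic nor the Section 2.2 text says which vaccination is meant.

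**Interim analysis.** Section 2 says: "Following collection of the 28 day post-vaccination clinical data and rapid measurement of serum IgG ELISA antibody levels, there will be an interim analysis" before Part 2. It names no dose and gives the SMC no role.

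**Benchmark.** Section 10.3 selects for Part 2 the highest dosage with at most one solicited symptom of grade 2 or above in the same category.

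**Halting.** Under Section 7.3, when a rule is met "the study will not proceed with the remaining enrollment or dose escalation without a review by and recommendation from" the SMC. The PI or sponsor may also halt at their discretion.

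**The concern.** Read together, these sections let the trial open a 25-person two-dose arm without any independent body having been required to look at the reactions that the two-dose regimen exists to measure. The Day 36 memory-aid data from Cohort C will have been collected, but no text sends them to the SMC.

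The second issue is what a halt stops. In a two-dose cohort the people most exposed after a safety signal are those already enrolled who are waiting for dose 2. The halting action speaks of enrollment and escalation only, so the site has no written instruction on whether to give those doses while the SMC deliberates.

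**Working it through.** **Cohort sizes.** From Section 2: A 8 + 2 = 10; B 10 + 2 = 12; C 6 + 6 + 4 + 4 + 2 = 22; D 25 + 25 + 10 = 60. Part 1 is 10 + 12 + 22 = 44 and the total is 44 + 60 = 104, as the protocol states. Participants who receive vaccine as dose 2 number 6 (25 mcg) + 4 (12.5 mcg) = 10 in Cohort C and 25 in Cohort D.

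**Timing.**

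| Event | Study day |
|---|---|
| Section 7.4 data cut (dose 1 + 7 days) | 8 |
| Dose 2 | 29 |
| Dose 2 reactogenicity visit | 36 |
| 28 days after dose 1 | 29 |
| 28 days after dose 2 | 57 |

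The only SMC data cut that names a dose ends 29 − 8 = 21 days before dose 2. The schematic has three gates (after A, B and C) and Section 7.4 has three meetings, so none is left for dose 2. If the interim analysis counts from dose 1, it closes on the day dose 2 is given.

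**Halting rules against the benchmark.** For non-serious clinical reactions, Section 7.3 needs grade 3 events in at least 2 participants (systemic toxicity or fever) or at least 3 (local pain or induration). The Section 10.3 benchmark is exceeded by 2 events of grade 2 in one category. Any number of grade 2 clinical reactions, up to 6 of 6 at 25 mcg, therefore exceeds the benchmark from the second one on and meets no clinical halting rule. The one halting rule set at grade 2 concerns laboratory values, and Section 7.1 schedules no safety laboratory tests after dose 2.

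**How likely is a breach?** The protocol gives no second-dose rate, so the rates p below are assumptions for one symptom at grade 2 or above. With X ~ Bin(6, p), P(X ≥ 2) = 1 − (1 − p)^6 − 6p(1 − p)^5.

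| Assumed p | (1 − p)^6 | 6p(1 − p)^5 | P(X ≥ 2) |
|---|---|---|---|
| 0.10 | 0.531 | 0.354 | 0.114 |
| 0.20 | 0.262 | 0.393 | 0.345 |
| 0.30 | 0.118 | 0.303 | 0.580 |
| 0.50 | 0.016 | 0.094 | 0.891 |

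Even with 6 people a breach is plausible at moderate rates. A clean result would reassure only partly: zero events in 6 leaves a one-sided 95% upper limit of 1 − 0.05^(1/6) = 39%, and zero in 10 leaves 26%.

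**Pending second doses.** If a rule is met once all 22 Cohort C participants are enrolled and none has yet had dose 2, 10 second vaccine doses are outstanding. Section 7.3 would block Part 2 but would not expressly block those doses. In the same position with all 60 of Cohort D enrolled, 25 are outstanding and no enrollment or escalation remains for the rule to stop.

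**The case against.** - **Section 10.3 already names the SMC.** Its dose-escalation criterion uses a similar grade 2 threshold, applies to any dose of vaccine, and lets the SMC recommend otherwise. That is true, but the sentence concerns moving to the next higher dosage cohort. It assigns no second-dose data to anyone, and Part 2 is an expansion at a selected dose.
- **The benchmark binds regardless of the halting rules.** If second-dose data were in hand and showed 2 of 6, 25 mcg should not be selected. This stands. The gap is that nothing fixes when those data are cut or has an independent body judge them.
- **The interim analysis may already cover dose 2.** Sections 2.2, 2.3 and 7.1 tie 28-day follow-up to each dose or to the last one. On that reading Cohort C's window closes at Day 57 and includes the Day 36 data. The reading is possible, but it still gives the SMC no role, and Section 7.4 is the only text that names a dose for the committee.
- **Prior concern is modest.** The SMC does see first-dose data on 6 + 6 = 12 recipients of 25 mcg. The background cites a well-tolerated two-dose 25 mcg Vi conjugate in children and four uneventful doses in rabbits. The probabilities above therefore matter only for reactions that first appear, or worsen, after dose 2. That is the question the protocol itself poses.
- **Other safeguards exist.** Halting rules are not limited to dose 1, the independent monitor reviews SAEs in real time, and eligibility is confirmed before dose 2. These cover serious events and individual participants. They do not reach a cluster of grade 2 reactions, and none expressly pauses second doses across the study.
- **Part 2 may never run.** The synopsis says vaccine may be lacking. Without Part 2 the first half of the point has no effect, but the pending-dose half still applies to Cohort C.

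**Conclusion.** The concern holds in both parts. The protocol can be followed exactly with no scheduled SMC review of second-dose reactogenicity in the 10 Cohort C recipients (6 at 25 mcg) before 25 more people are assigned to two doses. A met halting rule does not expressly suspend up to 10 second vaccine doses in Cohort C or 25 in Cohort D; PI or sponsor discretion is the only study-level brake on them.

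The 11% to 89% range rests on assumed rates. The counts of 10 and 25 are maxima, reached only if the rule is met after enrollment is complete and before any second dose. The finding is about what the plan requires: a careful sponsor might show the SMC these data, or pause dosing, without being told to. It is a cheap improvement to stated rules and does not undermine the design.

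**What to change.** 1. **Sections 2.2 and 7.4.** State that the SMC review that opens Part 2 includes Cohort C solicited adverse events through 7 days after dose 2 (the Day 36 visit), judged against the Section 10.3 benchmark.
2. **Section 7.3.** Extend the halting action to cover remaining enrollment, dose escalation and any further vaccination, including pending second doses.

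**Cost of the first change.** It adds no participants, visits or procedures. The SMC data cut moves from Day 8 to Day 36. The decision on Part 2 must already wait for the interim analysis, so against a Day 29 interim the net delay is 36 − 29 = 7 days, plus SMC meeting time. At the extremes of the visit windows it is 35 − 32 = 3 to 37 − 26 = 11 days. The Day 29 ELISA work would use some of that time; its turnaround is not stated. If the interim's 28 days run from dose 2 (Day 57), there is no delay. Any delay counts against a vaccine lot with limited shelf life, but arises only if supply lets Part 2 run.

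**Cost of the second change.** None unless a rule is met. If one is met, some second doses may fall outside the Day 29 ± 3 window, so the amendment should say how late doses are handled.
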